#### Procedure variables

- **Physician who performs the test** (Type of variable: Nominal qualitative) The professional who carries out the procedure.
- **Degree of experience of the physician** (Type of variable: Ordinal qualitative):
  - o Low: 5-20 procedures performed.
  - o Normal: 20-50 procedures performed.
  - o Discharge: >50 procedures performed.
- **Test Duration** (Variable Type: Continuous Quantitative) The total time of the procedure, which could correlate with the pain experienced.
- Use of the outer sheath (return) (Dichotomous qualitative: Yes/No)
- **Bipolar energy use** (Variable type: Qualitative dichotomous) Yes/No. The use of bipolar energy could influence pain due to the impact on the tissues.
- Number of polyps removed (Variable Type: Discrete Quantitative) 1, 2 or
- >2. The number of polyps could affect the level of pain due to time and additional manipulation.
- Number of biopsies taken (Variable Type: Discrete Quantitative) 1, 2 or
- >2. More biopsies may increase discomfort during and after the procedure.
- **Type of endometrial pattern** (Type of variable: Nominal qualitative) Atrophy, proliferative, menstrual or secretory. Different endometrial patterns can influence pain perception.
- **Number of Cavity Entries** (Variable Type: Discrete Quantitative) The number of times the hysteroscope needs to be inserted into the uterine cavity may be influence in the pain.
- **Insertion technique** (Variable type: Nominal qualitative) Direct entry vs. with speculum and forceps. Insertion techniques could have different implications on perceived pain.

## Variables of post-procedure pain

- VAS Scale (Visual Analog Scale) (Type of variable: Continuous quantitative) Range 0-10. To measure the intensity of the pain experienced by the patient.
- **Need for post-procedure analgesia** (Type of variable: Qualitative dichotomous) Yes/No. And **type of pain reliever used**.
- Size of the speculum Used (Type of variable: qualitative) (Small/medium/large). May influence the overall pain of the procedure
  - **Complications** (Type of variable: Qualitative dichotomous) Yes/No. Complications that occur during or after the procedure will be recorded.
  - **Complication Type** (Variable Type: Open-Label Qualitative) Details about the nature of the complication (if any).
  - **Indication for surgical hysteroscopy due to pain** (Type of variable: Qualitative dichotomous) Yes/No. If additional surgical intervention is required after hysteroscopy.

In addition, the patient's medical and personal history, as well as allergies, will be collected in the Medical Record to determine if there are contraindications to the procedure. All previously established inclusion and exclusion criteria will also be explored.

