## HARP Assay: Hysteroscopy Anesthesia for Relief of Pain

#### Introduction

Ambulatory hysteroscopy is a diagnostic technique commonly used in gynecology for the evaluation of the female reproductive tract, especially for the detection and treatment of intrauterine pathology. Although generally well tolerated, the management of pain associated with this procedure remains a relevant concern for many patients. Proper pain control is critical to improving the patient experience, reducing anxiety, and avoiding complications related to discomfort during the procedure. Pain, among other factors, is precisely one of the main reasons for failure of the procedure (Pascual Pedreño et al., 2021).

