## Importance of a well-designed clinical trial.

A well-designed randomized clinical trial has the ability to reduce biases and provide more robust evidence on the efficacy of interventions, such as anesthesia, in reducing pain during hysteroscopy. In this sense, the study design should include a representative sample of patients, a standardized method of pain assessment (such as the VAS scale), and strict control of confounding variables that may influence pain perception, such as the professional's experience, previous anxiety, and the type of intervention.

Through a more rigorous design, the study will also be able to identify predictors of pain and contribute to the development of evidence-based recommendations for pain management in hysteroscopy. This evidence is critical, as it not only improves the quality of the procedure, but also has the potential to optimize the patient experience, improving treatment adherence and reducing the need for general anesthesia.

In addition, variables that will give rise to new hypotheses will be included, such as the "indication of surgical hysteroscopy for pain". Knowledge of this data will allow later, according to the results obtained in the trial and after analysing the costs per procedure, to carry out new cost-effectiveness studies and assess whether anaesthesia can really be an efficient strategy in the face of non-application of anaesthesia.

For all these reasons, this study is of great relevance for the field of gynecology and ambulatory surgery, since it will specifically address the gaps in the existing literature on pain management during hysteroscopy, strengthening the quality of the evidence in this field. This is essential to improve clinical practice, offering a solid basis for decision-making in pain management in outpatient gynecological procedures.

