## Complex procedures:

- Morcellator myomectomies: More complex surgical procedures, such as morcellator myomectomy, are excluded because of their level of invasion and difficulty, which could interfere with the isolated assessment of anesthesia-associated pain.
- Failure to access the uterine cavity: If adequate access to the uterine cavity is not achieved, the procedure is considered incomplete and the patient will be excluded from the study.
- Situations that prevent access to the cavity: Patients in whom hysteroscopy is failed, with cervical stenosis or other anatomical defects that completely prevent adequate access to the uterine cavity will be excluded.
- Long interventions with a large fluid passage or water balance above 1000 cc: In these cases the patient may experience additional pain due to other circumstances unrelated to the routine procedure.
- **Known uterine malformations**: Patients with uterine malformations (such as septate, unicornuate, or bicornuate uterus) will be excluded, as this could complicate access and interpretation of results, as well as affect pain tolerance during hysteroscopy.
- Waiting times longer than 60 minutes: It has been associated with an increase in pain according to the SEGO guideline for ambulatory hysteroscopy.
   Taking analgesic medication before the test: Taking medication before the test may alter the results.
- Major complication associated with the intervention: Uterine perforation, creation of false pathway or false endocervical pathway or intense bleeding (expressed as hemorrhage that requires additional maneuvers than usual for resolution).
- Failure to provide adequate informed consent in consultation or the anxiety assessment scale prior to the procedure.

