## Patients excluded from the study:

If a patient, after being included, is subsequently rejected from participating, any data related to her will be removed from the clinical trial.

The reason for exclusion will be recorded for further analysis.

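### The item on surgical hysteroscopy due to pain is explained without pain, and patients whose cavity cannot be accessed because of pain lose their data, so the count meant for later cost work is ambiguous and incomplete

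*Protocol*

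**What the plan says.** Under *Variables of post-procedure pain* the protocol lists a dichotomous item labelled "Indication for surgical hysteroscopy due to pain". The only explanation given is "If additional surgical intervention is required after hysteroscopy". The list has no separate item for surgery needed for another reason.

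*Importance of a well-designed clinical trial* names the item as one that should generate hypotheses, and gives its later use: "to carry out new cost-effectiveness studies and assess whether anaesthesia can really be an efficient strategy". The rationale section before it describes the event of interest, namely patients who tolerate the office procedure badly because of pain and then need it under sedation in the operating room. The *Introduction* adds: "Pain, among other factors, is precisely one of the main reasons for failure of the procedure".

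The exclusion criteria, under *Complex procedures*, remove any patient in whom adequate access to the cavity is not achieved, without regard to cause. A further bullet removes "Patients in whom hysteroscopy is failed, with cervical stenosis or other anatomical defects" where these completely prevent access. *Patients excluded from the study* then says that, for a patient excluded after inclusion, "any data related to her will be removed from the clinical trial"; the reason for her exclusion is recorded. *Analysis by Protocol* restricts the analysis to patients who complete the study and drops incomplete or non-compliant data. None of these sections makes an exception for this item.

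**The concern.** Two separate faults affect the same item.

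- **Coding.** The label requires pain and the explanation does not. A comfortable patient referred to theatre for a lesion unsuited to the office is No by the label and Yes by the explanation. Two people filling in the spreadsheet could code her differently.
- **Observability.** A patient in whom pain prevents entry to the cavity is a clear case of what the item is meant to count. She is excluded after randomisation, on the basis of something that anaesthesia may influence, and her data are taken out.

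At stake is the count that later cost-effectiveness work would start from. Events that were removed or coded ambiguously cannot be restored by any later analysis. The point concerns this one item, not the analysis set for the VAS.

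**Working it through.** **Stated figures.** The protocol gives no rate, target or sample size for this item. Its only calculated figure is for the VAS: difference 1.5, SD 2.0, 5% significance and 80% power, giving 29 per group. An exact two-sided t-test with d = 1.5/2.0 = 0.75 needs 28.9 per group, so 29 reproduces. It is used below only to count expected events.

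**Sequence of rules.**

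1. *Randomization process* places allocation after consent. It mentions both presentation for the intervention and the consultation at which the test is indicated. Either way it comes before the procedure.
2. Failed access is discovered during the procedure, so that exclusion is always after randomisation.
3. Her data are removed and only a reason is kept. *Randomization process* has the group written in the clinical record, but nothing says that it stays with the exclusion reason in the trial data.
4. The access criterion names no cause, so a recorded reason of failed access need not say whether pain or stenosis was responsible.
5. A patient stopped by pain after entry is not excluded by the access criterion. She may still be dropped under *Analysis by Protocol* if her data count as incomplete.

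**Effect on the recorded rate.** Let p be the true rate of pain conversion, f the share of those patients deleted, and q the rate of other surgery coded Yes among the remaining patients. All three are assumptions, because the documents give none of them.

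Recorded rate = [(1 − f)p + q(1 − p)] / (1 − fp)

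Take p = 10% (control) v 5% (anaesthesia), f = 0.5 and q = 0:

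- Control: 0.5 × 0.10 / (1 − 0.05) = 0.050/0.950 = 5.3%
- Anaesthesia: 0.5 × 0.05 / (1 − 0.025) = 0.025/0.975 = 2.6%

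| Share deleted, f | q = 0 | q = 10% in both arms |
|---|---|---|
| 0 | 10.0% v 5.0% | 19.0% v 14.5% |
| 0.5 | 5.3% v 2.6% | 14.7% v 12.3% |
| 0.8 | 2.2% v 1.0% | 12.0% v 10.9% |
| 1.0 | 0% v 0% | 10.0% v 10.0% |

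With q = 0 and f = 0.5, 0.8 and 1.0, a true difference of 2.5 points (5% v 2.5%) becomes 1.3, 0.5 and 0 points. A true difference of 10 points (20% v 10%) becomes 5.8, 2.6 and 0 points.

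**Unequal deletion.** The share deleted need not be the same in both arms. Combining entries from the q = 0 column, f = 0.8 in control and 0.5 with anaesthesia gives 2.2% v 2.6%, which reverses the order. The opposite pattern gives 5.3% v 1.0%, which exaggerates the difference.

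**Number of events.** With nobody deleted, 10% v 5% at 29 per arm means 29 × 0.10 = 2.9 and 29 × 0.05 = 1.45 events. Power to detect that difference would be about 11%.

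**The case against.** The strongest reply is that the text is better than it looks.

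- **The label still says pain**, and so does the rationale. A reader might infer that the item is defined as any further surgery. The documents do not support that: label and explanation disagree, and a coder who follows the label gets it right. What stands is the contradiction.
- **Deletion is tied to cavity access.** A reader might infer that every patient stopped by pain is deleted. The protocol does not say so. The bullet on failed hysteroscopy concerns stenosis and anatomical defects, and a patient stopped during polypectomy or biopsy, or referred to theatre after the diagnostic part, is not expressly excluded. What stands is the loss of pain failures before entry, and possibly of some later ones as incomplete data.
- **Reasons for exclusion are kept**, and the investigators' commitment repeats this. That helps only if the reason identifies pain and can be linked to arm, and neither is stated.
- **The item is exploratory.** The primary endpoint is the VAS, no between-arm test of this item is stated, and events would be few even with full capture. This limits the seriousness. It does not excuse the wrong numerator and denominator in a count meant for later use.
- **The illustration rests on assumed rates.** This is correct. Equal recorded rates of 10.0% v 10.0% arise only if every pain conversion is deleted and other surgery at 10% in each arm is coded Yes against the label. With half deleted and the label followed, the roughly twofold ratio survives.

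**Conclusion.** The point holds in a limited form. The explanation contradicts the label by leaving out pain, so unrelated surgery may be counted. Patients in whom pain prevents access to the cavity are excluded after randomisation with their data removed, so some true events are lost, and the loss may differ by arm.

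The direction follows from the text when the share deleted is similar in both arms: the recorded absolute difference shrinks. With unequal deletion it can move either way. The size depends wholly on assumed rates and on the share of pain conversions that occur before entry. The documents do not support saying that the item records only the wrong patients, or that it must show no difference.

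The harm is an undercounted and ambiguously coded input to later cost-effectiveness work. This point does not show a biased main conclusion. It is still worth correcting, because it concerns what is collected and retained.

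**What to change.** 1. In *Variables of post-procedure pain*, redefine the item as a further hysteroscopy, in the operating room or under sedation, indicated because of pain or intolerance.
2. Add a separate item for surgery indicated for any other reason.
3. In *Complex procedures*, *Patients excluded from the study* and *Analysis by Protocol*, state that arm, this outcome and the reason for stopping (pain; stenosis or anatomy; other) are kept for every randomised patient who starts the procedure, including those with failed access.
4. State that the item is reported descriptively by arm, with those patients as the denominator.

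The cost is one reworded item, an extra column for other surgery, a coded reason for stopping, and a retention sentence in three places. It needs no extra patients or visits and no change to treatment. The small downside is that the operator must attribute the reason for stopping, which takes judgement and is made by someone who knows the arm.

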## Sample size calculation

Variables used in the calculation.

**Primary study endpoint**: Pain measured using the VAS scale (0-10).

Since we compared two groups (with anesthesia vs. without anesthesia) on a continuous quantitative variable (VAS), we will use a Student's t-test for independent samples (or Mann-Whitney U if the distribution is not normal).

## **Clinically Relevant Difference:**

• In previous studies, a reduction of at least 1.3 - 1.5 points in VAS has been considered to be clinically meaningful in gynecological procedures. □ Proposal: Establish an expected difference of 1.5 points in the VAS.

**Standard deviation** of pain in hysteroscopy without anesthesia:

According to previous studies, the standard deviation of pain ranges from 1.8 to 2.5 points in VAS.

Proposal: Use a standard deviation ( $\sigma$ ) of 2.0 for the calculation.

## Level of significance:

It is set at 5% (0.05), which implies a probability of type I error of 5% (rejecting the null hypothesis when it is true).

## **Statistical power:**

The statistical power is set at 80% (0.8), which implies a 20% probability of type II error (not detecting a real difference).

#### **Final Estimate**

To calculate the sample size in a clinical trial comparing pain in two groups (with and without anesthesia), we used the formula to compare two independent means. The effect size (Cohen's d) is obtained by dividing the clinically relevant difference by the standard deviation, obtaining a moderate-high effect size according to Cohen's classification.

Using a t-test for two independent samples, the sample size that provides the desired power is sought. When the information is entered into sample size calculation software, the result is a sample size of 29 patients per group. This means that the study will need a total of **58** patients.

If follow-up losses are anticipated, it is recommended to increase the sample size by 10-20%. Therefore, it would be advisable to include between **64 and 70 patients** in total to ensure adequate statistical power.

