## Objectives of the study

The aim of the study is to demonstrate whether locoregional anaesthesia has an impact on the pain perception of patients who undergo ambulatory hysteroscopy, i.e. to demonstrate whether there are significant differences in pain perception in patients who undergo such anaesthesia and those who do not.

H0: Half pain (VAS) analgesia = half pain (VAS) without analgesia

As secondary objectives, if differences are demonstrated, we will try to show which variables interfere with the patient's pain through a logistic regression analysis.

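### The allowance for losses multiplies 58 by 1.10 to 1.20 (64 to 70) instead of dividing by the fraction retained, and no single recruitment target is fixed; the shortfall in power is small

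*Protocol*

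**What the plan says.** Under Sample size calculation, the protocol sets significance at 5% and power at 80%. For the effect it says "Establish an expected difference of 1.5 points in the VAS", with a standard deviation "of 2.0 for the calculation". Final Estimate reports 29 patients per group from a two-sample t-test, 58 in total.

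The same section then turns to losses: "it is recommended to increase the sample size by 10-20" percent. It concludes that between 64 and 70 patients would be advisable "in total to ensure adequate statistical power". It gives no expected loss rate as such and does not choose a number within the range.

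Several later sections reduce the number analysed:

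- **Complex procedures (exclusion criteria).** This lists events that can be known only at or around the hysteroscopy. For failed access to the cavity, for example, "the procedure is considered incomplete and the patient will be excluded from the study".
- **Patients excluded from the study.** Data of patients rejected after inclusion are removed.
- **Analysis by Protocol (3.1).** The analysis is limited to completers once the necessary sample size is reached, and incomplete or non-compliant data are dropped. It does not say whether the necessary size is 58, 64 or 70.

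**The concern.** An allowance for losses is meant to leave the required number after the losses have occurred. Losses are a fraction of those enrolled, so the required number must be divided by the fraction retained. Adding the same percentage to the required number always falls short, and by more as the loss rate rises.

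The planned 29 per group has almost no slack, so any shortfall takes power below the stated 80%, while the section offers its range as securing that power. The range also does not say when recruitment ends: a team could stop at 64 or at 70 and follow the text either way.

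**Working it through.** **Inputs (protocol)**

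- Difference 1.5 and SD 2.0, so d = 1.5/2.0 = 0.75.
- Alpha 0.05. The number of sides is not stated. Two-sided is assumed because the null is an equality ("H0: Half pain (VAS) analgesia = half pain (VAS) without analgesia"). In the normal approximation, a one-sided test needs only 22 per group, which does not match the stated 29.
- Power 80%, 1:1 allocation, two-sample t-test.

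**Step 1. Reproduce the base figure.** The noncentral t calculation gives n = 28.90 per group, rounded up to 29. Power at 29 per group is 80.1%. The stated 29 and 58 are correct.

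**Step 2. Reproduce the range.** 58 × 1.10 = 63.8, rounded to 64. 58 × 1.20 = 69.6, rounded to 70. This is exactly the stated range.

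**Step 3. Total needed to retain 58.** N = 58/(1 − loss).

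- 10% loss: 58/0.90 = 64.4, so 65 (66 for equal arms).
- 20% loss: 58/0.80 = 72.5, so 73 (74 for equal arms).

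**Step 4. What the stated totals leave.**

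| Enrolled | Loss | Remaining | Power |
|---|---|---|---|
| 64 | 10% | 57.6 | 79.4% with 57, 80.1% with 58 |
| 70 | 20% | 56 | 78.7% |
| 70 | 10% | 63 | about 83% |
| 64 | 20% | 51.2 | about 75% |

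The first two rows match each end of the range to its own percentage. The last two are the extremes that the open range allows.

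**Step 5. Loss each total can absorb.** 1 − 58/64 = 9.4%. 1 − 58/70 = 17.1%.

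**The case against.** The strongest defence is that the protocol states an increase of 10-20%, not a loss of 10-20%, and 64 to 70 follows exactly from that instruction. This stands as a matter of wording. However, the sentence opens with anticipated losses and ends by promising power, so reading the percentage as the loss to be covered is natural.

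The second defence is that the effect is negligible. With matched ends, the shortfall from 58 is 0.4 to 2 patients, and power is at most 1.4 points below the 80.1% at 29 per group. The protocol's own SD range of 1.8 to 2.5 moves power at 29 per group from 87.7% to 61.2%, which matters far more. Any total from 65 to 70 fully covers a 10% loss. All of this stands and is why the point is minor.

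Third, Analysis by Protocol could mean that recruitment continues until 58 patients have completed, in which case the inflation formula costs no power. The wording allows that reading but does not establish it.

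A reader might infer that the trial will be materially underpowered, at about 75%, or that losses near 20% are to be expected. The documents support neither. The 75% pairs the lowest total with the highest percentage, a pairing that the protocol does not make, and the opposite pairing gives about 83%. The documents give no frequency for failed access, long waits or the other exclusions.

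**Conclusion.** Wrong as written, of minor severity. The range of 64 to 70 is the base figure multiplied up, and it does not preserve 58 analysable patients at 10% and 20% loss respectively; 65 and 73 would. With matched ends, power is 79.4 to 80.1% at the lower end and 78.7% at the upper, so the assurance of adequate power is slightly too favourable rather than seriously misleading.

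The open target allows a wider spread, about 75% to about 83%, but this is mainly loose wording that a single stated number would close.

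The figures assume a difference of 1.5, SD 2.0, a two-sided 5% t-test and equal arms. Simple randomisation does not guarantee equal arms: with 58 analysed, power averaged over random splits is about 79.4%. The conclusion also rests on reading the 10-20% as a loss rate.

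**What to change.** In Final Estimate, state one expected loss rate and one recruitment target, computed as 58/(1 − loss). The rate should count the exclusions after randomisation described under Complex procedures, Patients excluded from the study and Analysis by Protocol, as well as follow-up losses. Since the protocol gives no frequency for these, the chosen rate should be labelled as an assumption. The target is 65 at 10% (66 for equal arms) or 73 at 20% (74 for equal arms).

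If the sponsor does not wish to enrol more than already planned, keep 70 as the single target. State that it preserves 58 analysable patients for losses up to 17%, and that power at 20% loss is 78.7%.

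Analysis by Protocol should then refer to that number and say whether it counts enrolled or analysable patients.

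The cost is a sentence or two of text. Keeping 70 adds no patients beyond the current upper figure, and the stated assurance becomes slightly less favourable. Using 20% adds three patients to that figure (73 − 70), or four for equal arms (74 − 70).
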